## **6.3** Clinical Laboratory Tests

Safety laboratory determinations will include hematology, blood chemistry, and urinalyses. All laboratory tests required during the study must be obtained at a primary laboratory designated by the Principal Investigator.

- Hematology: CBC including hemoglobin, hematocrit, white blood cell count with 5-part differential, red blood cell, platelet.
- Blood chemistry: HCO2, calcium, phosphorus, magnesium, albumin, glucose, and serum creatinine
- Liver function tests: AST, ALT, lactate dehydrogenase (LDH), alkaline phosphatase, total and direct bilirubin, uric acid, total protein and blood urea nitrogen (BUN)
- Electrolytes: sodium, potassium, and chloride
- Routine urinalysis: dipstick and microscopy including protein, specific gravity, glucose and blood
- Serum pregnancy test for female patients of childbearing potential.

### **6.4** Pharmacokinetic Assessments

Blood samples for the PK of BBI608 and Cetuximab, or Panitumumab, or Capecitabine will be collected from the first 6 patients enrolled in each combination arm. Approximately 30 blood samples for PK will be collected for each patient. Collection, storage, and shipping of PK samples will be performed as described in Appendix D.

# 6.5 Pharmacodynamic Assessments

Pre-clinical studies conducted BBI have identified several biomarkers in tumor tissues whose levels either increase or decrease upon exposure to BBI608. Tumor biopsies will be collected as described below provided the patient has accessible tumor and has signed the optional tumor biopsy consent. The goal of the proposed biomarker study is to examine the response of biomarkers in patients treated with BBI608. For tumor biopsies, tumor samples will be obtained before and after dosing in selected subjects. Subject tumor samples will be processed for determination of pharmacodynamic markers of in malignant tissue by histopathology and flow cytometry.

## 6.5.1 Tumor Biopsy

Patients who are identified by the Principal Investigator as having a lesion, which could be biopsied with a minimally invasive procedure, will be asked to sign an additional consent. Tumor samples should be collected at baseline and at 4 h after administration of the BBI608 morning dose on Day 8. Collection, storage, and shipping of tissue samples will be performed as described in Appendix E.

# 7 TREATMENT

### 7.1 BBI608

BBI608 capsules will be supplied to the pharmacy at the clinical sites. BBI608 will be labeled as an investigational agent, limited by federal law. The pharmacist will dispense an appropriate number of each strength capsule to the Principal Investigator for in-clinic dosing. The appropriate quantity of capsules will be dispensed to the patient depending on the combination regimen.

For the Cetuximab arm, the appropriate number of capsules will be dispensed for four days of daily dosing on day 1, 1 week of daily dosing on day 5, day 12, day 19, and day 26 during cycle 1, and for 1 month of daily dosing for cycle 2 and beyond at the prescribed dose, including two extra doses.

For the Panitumumab arm, the appropriate number of capsules will be dispensed for eight days of daily dosing on day 1, 2 weeks of daily dosing on day 8, and 2 weeks of daily dosing on day 21 during cycle 1, and for 1 month of daily dosing for cycle 2 and beyond at the prescribed dose, including two extra doses.

For the Capecitabine arm, the appropriate number of capsules will be dispensed for 1 week of daily dosing on day 1, 1 week of daily dosing on day 8, 1 week of daily dosing on day 15, 2 weeks of daily dosing on day 21, and for 1 month of daily dosing for cycle 2 and beyond at the prescribed dose, including two extra doses. These instructions must appear on the label for the container in which capsules are delivered to the patient.

Cetuximab, Panitumumab, and Capecitabine will be handled as described in the Product Labels approved by US FDA or Health Canada (see **Appendix F**).

## 7.1.1 Investigational Product Accountability

BBI will provide all BBI608 required for completion of this study. The recipient will acknowledge receipt of the drug indicating shipment content and condition. Damaged supplies will be replaced. Until dispensed to the patients, the study drug will be stored at room temperature, in a secure locked area, accessible to authorized personnel only.

Accurate records of all BBI608 dispensed from and returned to the study site are to be maintained. The study site must supply a copy of their drug destruction policy to BBI before authorization for destruction will be granted. Product accountability will be monitored throughout the study. Upon completion or termination of the study, and after inventory by a BBI monitor or designated representative, all unopened drug is to be returned to BBI or designee in the original containers.

## 7.1.2 BBI608 Administration

• BBI608 will be administered daily for 28 consecutive days. BBI608 will be administered twice daily, approximately one hour prior to or two hours after meals, with the first dose given in the morning.

## 7.1.3 Cetuximab, Panitumumab, or Capecitabine Administration

- Detailed instructions for the preparation, premedication, and administration of Cetuximab, Panitumumab, or Capecitabine are provided in the Product Labels approved by Health Canada or US FDA.
- Cetuximab will be administered via IV on Days 5, 12, 19 and 26 of a 28 day cycle, about 3 hours after the first daily dose of BBI608. Panitumumab will be administered via IV on Days 8, and 22 of a 28 day cycle, about 3 hours after the first daily dose of BBI608. Capecitabine will be administered orally twice-daily for two weeks out of three weeks. The first dose of Capecitabine should be taken about 3 hours after the first daily dose of BBI608 on day 8 of each 3 week cycle of Capecitabine.

# 7.1.4 Diarrhea Management

For each combination arm, treatment for BBI608-related diarrhea will be instituted on a prophylactic or on an as needed basis depending on sub-cohort assignment.

Patients assigned to sub-cohorts IA and IIA will receive prophylactic anti-diarrheal medication starting the day prior to day 1 of cycle 1. With development of intolerable grade 2 diarrhea or greater, prophylactic anti-diarrheal regiment may be adjusted as needed. Patients assigned to sub-cohorts IB and IIB will receive anti-diarrheal medication on an as needed basis starting with development of BBI608-related intolerable grade 2 or above diarrhea. Patients in all 4 sub-cohorts who develop sub-optimal diarrhea control while on protocol therapy will have adjustment of their anti-diarrheal regiment as needed.

The following treatments are suggested for diarrhea and accompanying abdominal cramping management:

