To evaluate the tolerability of BBI608, patients from each arm will be assigned to one of 4 sub-cohorts (with 6 patients in each sub-cohort IA, IB, IIA, IIB). The evaluation of tolerability will be done at select centers for the study arm that is continuing patient accrual and in which a total of 50 evaluable patients has not been reached. For each combination arm, patients assigned to sub-cohorts IA and IB will receive BBI608 at 240 mg po twice daily (480 mg total daily dose) starting on day 1 of cycle 1. Intrapatient dose escalation of BBI608 to 480 mg po twice daily (960 mg total daily dose) is allowed as tolerated. Patients assigned to sub-cohorts IIA and IIB will receive BBI608 at 480 mg po twice daily (960 mg total daily dose) starting on day 1 of cycle 1. In case of toxicity, dose adjustment of BBI608 is permitted, as recommended in dose modification guidelines. Additionally, patients assigned to sub-cohorts IA and IIA will receive prophylactic anti-diarrheal treatment starting the day prior to day 1 of cycle 1. Patients assigned to sub-cohorts IB and IIB will anti-diarrheal treatment on an as needed basis starting with development of diarrhea above baseline. For each combination regimen, patients will be sequentially assigned to each of the 4 subcohorts in the following order until 6 patients are accrued on each of the sub-cohorts: IA, IB, IIA, and IIB. If required, up to additional 20 patients may be assigned to selected sub-cohorts to validate the observations in initial 6 patients.

	Sub- cohort	BBI608 Starting Dose Level	Anti-diarrheal Administration	
	IA	240 mg bid (480 total daily dose) 	Prophylactic	
	IB	240 mg bid (480 total daily dose) 	As needed	
	IIA	480 mg bid (960 total daily dose) 	Prophylactic	
	IIB	480 mg bid (960 total daily dose) 	As needed	
	1	ent dose escalation of BBI608 to 480	mg po twice daily (960 mg total	
		) is allowed as tolerated  Stoxicity, dose adjustment of BBI608 is	permitted.	
Study Population:	This study will enroll patients with advanced colorectal cancer. Patients must have received at least 2 lines of standard chemotherapy based on regimens containing 5-FU, irinotecan or oxaliplatin. Patients to be enrolled into the Cetuximab or Panitumumab combination arms must have colorectal cancer with wild-type K-Ras.  Patient accrual will occur over a period of time dependent upon the enrollment rate of the study.			

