## 2.2 Secondary Objectives

The secondary objectives of the study are:

- To determine the pharmacokinetic profile of BBI608 and Cetuximab, or Panitumumab, or Capecitabine when administered in combination.
- To determine the pharmacodynamics (biomarkers) of BBI608.
- To evaluate tolerability of two dosing regimens of BBI608 by comparing administration of BBI608 at 240 mg twice daily starting dose and escalating to 480 mg twice daily after cycle 1 versus administration of BBI608 at 480 mg twice daily starting dose with dose adjustment permitted.
- To evaluate tolerability of BBI608 by comparing prophylactic administration of anti-diarrheal medication versus as needed administration of anti-diarrheal medication. The tolerability will be assessed using adverse event profile and achieved dose intensity.

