**Table 2 Disease Control Rate – Third Line** 

	Monotherapy (Historical)	Combination * (Historical)	Combination with BBI608 (Expected)
Cetuximab	30-40% 	~ 63% 	60% or more
Panitumumab	30-40% 	~ 68% 	60% or more
Capecitabine	~ 15% 	~ 45% 	60% or more

\* Cetuximab + Irinotecan
Panitumumab + Irinotecan
Capecitabine + Mitomycin C

For the Cetuximab and Panitumumab combination cohorts, if the disease control rate in stage 1 reaches 3 of 8 or above, additional patients will be enrolled into the stage 2 cohort. For the

Capecitabine combination cohort, if the disease control rate in stage 1 reaches 2 of 6 or above, additional patients will be enrolled into the stage 2 cohort.

To evaluate the tolerability of BBI608, patients from each arm will be assigned to one of 4 subcohorts (with 6 patients in each sub-cohort IA, IB, IIA, IIB). The evaluation of tolerability will be done at select centers for the study arm that is continuing patient accrual and in which a total of 50 evaluable patients has not been reached. For each combination arm, patients assigned to sub-cohorts IA and IB will receive BBI608 at 240 mg po twice daily (480 mg total daily dose) starting on day 1 of cycle 1. Intra-patient dose escalation of BBI608 to 480 mg po twice daily (960 mg total daily dose) is allowed as tolerated. Patients assigned to sub-cohorts IIA and IIB will receive BBI608 at 480 mg po twice daily (960 mg total daily dose) starting on day 1 of cycle 1. In case of toxicity, dose adjustment of BBI608 is permitted, as recommended in dose modification guidelines. Additionally, patients assigned to sub-cohorts IA and IIA will receive prophylactic anti-diarrheal treatment starting the day prior to day 1 of cycle 1. Patients assigned to sub-cohorts IB and IIB will anti-diarrheal treatment on an as needed basis starting with development of diarrhea above baseline. For each combination regimen, patients will be sequentially assigned to each of the 4 sub-cohorts in the following order until 6 patients are accrued on each of the sub-cohorts: IA, IB, IIA, and IIB. If required, up to additional 20 patients may be assigned to selected sub-cohorts to validate the observations in initial 6 patients.

Table 3 Tolerability Analysis of BBI6	U8
---------------------------------------	----

Sub-cohort	BBI608 Starting Dose Level	Anti-diarrheal Administration

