### 10.8 Analysis and Sample size for sub-cohorts

Each sub-cohort will be analyzed for number of days of Grade II/III diarrhea and % treatment compliance achieved during the first two cycles. The % treatment compliance will be calculated as the number of capsules actually ingested over the number of capsules that should have been ingested per dose level multiplied by 100. The research questions addressed by sub-cohorts are hypothesis-generating and exploratory in nature. Initially 6 subjects will be assigned to each sub-cohort to assess the effect of intervention. Selected sub-cohorts will be extended to enroll up additional 20 patients. The decision of extending the enrollment will be based on clinical assessment without formal statistical testing. However, 20 patients will give 80% power to detect 20% difference in % treatment compliance between two arms and 57% power to detect the difference of 25% in the number of days of having Grade II/III diarrhea using two-sided Z test with pooled variance at type I error rate of 0.15. The control rates assumed are 70% for treatment compliance and 30% for diarrhea. The patients will be sequentially allocated to different sub-cohorts by the Sponsor to avoid section bias.

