combination arm, patients assigned to sub-cohorts IA and IB would receive napabucasin at 240 mg twice daily (480 mg total daily dose) starting on Day 1 of Cycle 1. Intra-patient dose escalation of napabucasin to 480 mg twice daily (960 mg total daily dose) was allowed for patients in these cohorts as tolerated. Patients assigned to sub-cohorts IIA and IIB would receive napabucasin at 480 mg twice daily (960 mg total daily dose) starting on Day 1 of Cycle 1. In the event of toxicity, dose adjustment of napabucasin was permitted, as recommended in dose modification guidelines. Additionally, patients assigned to sub-cohorts IA and IIA would receive prophylactic anti-diarrheal treatment starting the day prior to Day 1 of Cycle 1. Patients assigned to sub-cohorts IB and IIB would receive anti-diarrheal treatment on an as-needed basis starting with development of diarrhea (ie, any occurrence greater than the patient's baseline). For each combination regimen, patients would be sequentially assigned to each of the 4 sub-cohorts in the following order until 6 patients were accrued in each of the sub-cohorts: IA, IB, IIA, and IIB. If required, up to an additional 20 patients might be assigned to selected sub-cohorts to validate the observations in the initial 6 patients.

Sub-cohort	Napabucasin Starting Dose Level	Anti-diarrheal Administration*
IA	240 mg bid (480 total daily dose) ¹	Prophylactic
IB	240 mg bid (480 total daily dose) ¹	As needed
IIA	480 mg bid (960 total daily dose) ²	Prophylactic
IIB	480 mg bid (960 total daily dose) ²	As needed

Table 1 Tolerability Analysis of Napabucasin

¹Intra-patient dose escalation of napabucasin to 480 mg po twice daily (960 mg total daily dose) is allowed as tolerated. ²In case of toxicity, dose adjustment of napabucasin is permitted.

*See protocol amendment 2 [5] section 7.1.4 for details

A study cycle would consist of 28 days of daily administration of napabucasin in combination with cetuximab or panitumumab, or capecitabine. Cycles would continue until unacceptable toxicity, disease progression (clinical or radiological) or another discontinuation criterion is met. Pharmacokinetic (PK) assessments would be performed on the first 6 patients enrolled in each combination arm. Pharmacodynamic assessments would be performed in patients with readily accessible tumor tissue through an optional tumor biopsy. Evaluation of anti-tumor activity would be performed at 8-week intervals per RECIST 1.1 while patients remain on study.

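### The start rule for as-needed anti-diarrheal treatment in sub-cohorts IB and IIB is given in two incompatible forms, which leaves the comparator of an exploratory secondary objective with an ambiguous threshold

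*Protocol*

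**What the plan says.** One secondary objective (protocol 2.2, repeated in SAP 2.1.2) evaluates tolerability by "comparing prophylactic administration of anti-diarrheal medication versus as needed administration of anti-diarrheal medication". Sub-cohorts IA and IIA take prophylaxis from the day before day 1 of cycle 1. IB and IIB are treated as needed.

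The as-needed start rule appears in four places:

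- Protocol synopsis, Study Design: "as needed basis starting with development of diarrhea above baseline".
- Protocol 4.1: "on an as needed basis starting with development of diarrhea above baseline".
- SAP 2.1: "starting with development of diarrhea (ie, any occurrence greater than the patient's baseline".
- Protocol 7.1.4: "starting with development of BBI608-related intolerable grade 2 or above diarrhea".

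Under its sub-cohort table, SAP 2.1 also refers the reader to the last of these: "See protocol amendment 2 [5] section 7.1.4 for details".

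On the endpoint, protocol 10.8 states "Each sub-cohort will be analyzed for number of days of Grade II/III diarrhea", together with treatment compliance, over the first two cycles. SAP 8.2.4.1 summarizes days of diarrhea of Grade II or above and gives no two-cycle window.

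**The concern.** The start rule is what defines an as-needed strategy, so two rules describe two interventions. Neither text can be read as an elaboration of the other: one has no condition beyond exceeding baseline, while the other adds a minimum grade, intolerability and attribution to BBI608.

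The disagreement also falls on the endpoint's own threshold. The endpoint starts counting at Grade II, and one rule permits treatment below that level while the other does not. Part of any difference between the prophylactic and as-needed sub-cohorts in diarrhea days could then reflect which section a site followed. The tolerability evaluation runs at selected centers with six patients per sub-cohort, and the decision to extend a sub-cohort rests on clinical assessment without formal testing. Nothing in the planned outputs would show which rule was applied.

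**Working it through.** **The plan's own figure.** Protocol 10.8 gives 57% power for a 25% difference in diarrhea days, with 20 patients, a two-sided pooled Z test at 0.15 and a control rate of 30%. Reading this as 20 per group and as proportions:

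power = Φ{[d − z·√(2p̄(1−p̄)/n)] / √([p1(1−p1) + p2(1−p2)]/n)}, with z = 1.44.

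- 30% against 55%: p̄ = 0.425, so Φ{(0.25 − 1.44 × 0.1563)/0.1512} = 56.6%. This reproduces 57%.
- 30% against 5%: p̄ = 0.175, so Φ{(0.25 − 1.44 × 0.1202)/0.1135} = 75.1%. This does not.

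The 30% control rate is not tied to either trigger. Resolving the contradiction therefore changes no stated number, and the figure does not help to size the problem. The point rests on wording.

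**The two rules side by side.** Neither endpoint definition restricts the counted days to diarrhea that is intolerable or attributed to BBI608. For a patient in IB or IIB whose diarrhea is above baseline:

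| Situation | Synopsis, 4.1, SAP 2.1 | Protocol 7.1.4 | Endpoint day? |
|---|---|---|---|
| Grade 1 | Starts | Does not start | No |
| Grade 2 or 3, tolerable | Starts | Does not start | Yes |
| Grade 2 or 3, intolerable, not attributed to BBI608 | Starts | Does not start | Yes |
| Grade 2 or 3, intolerable, attributed to BBI608 | Starts | Starts | Yes |

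The rules agree only in the last row. In the first row, the above-baseline rule allows treatment before any endpoint day has occurred. In the second and third rows, endpoint days accrue with treatment started under one rule and not under the other. Any as-needed patient who starts under 7.1.4 is already in the endpoint's range.

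**How many patients.** Two as-needed sub-cohorts of 6 give 12 of the 24 planned sub-cohort patients per combination arm. If all three arms take part, that is 36 of 72, before the optional extension of up to 20 in selected sub-cohorts.

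**Size of the effect.** The shift in a sub-cohort's mean would be f × w. Here f is the fraction of its patients for whom the choice of rule changes when treatment starts, and w is the mean number of Grade II or higher days avoided in them by the earlier start. The documents give neither. With f anywhere from 0 to 1, the shift lies between 0 and w, and w is unknown.

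**The case against.** Protocol 7.1.4 might be taken to govern, since it is the operational section on diarrhea and the SAP footnote sends the reader there. That does not settle the matter: the text of SAP 2.1 restates the above-baseline rule explicitly, and no section sets an order of precedence.

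The stronger objection concerns weight, and much of it stands. Protocol 10.8 labels the sub-cohort questions exploratory, allocation is sequential and non-randomized, and SAP 4.1 disclaims hypothesis testing. Protocol 2.2 assesses this objective by adverse event profile and achieved dose intensity, not by diarrhea days alone. Protocol 7.1.4 also lets all four sub-cohorts adjust their anti-diarrheal regimen when control is poor, which blurs the strategies under either trigger.

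A reader might infer that the comparison has no defined comparator at all. The documents do not support that. Under either rule, IA and IIA begin before the first dose and IB and IIB begin only after diarrhea appears, so the contrast survives. What is undefined is the threshold within the as-needed strategy. Nor do the documents show that sites actually used different rules; they only make it possible.

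**Conclusion.** The contradiction is real and stands in the current text of both documents. It leaves the as-needed comparator with an ambiguous threshold, placed where it bears on the diarrhea-days endpoint. It should be corrected, but its weight is limited to an exploratory secondary objective; the primary disease control endpoint is not directly affected.

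That the endpoint would differ between the two rules is an inference from the definitions, and it assumes that earlier treatment can avert some Grade II or higher days. A reader might be tempted to put a figure in days on the shift in a six-patient mean. The documents give no diarrhea rate under either trigger, no delay to treatment and no effect of early treatment, so any such figure would be the reader's own assumption. No view is taken on which trigger is clinically right.

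**What to change.** Reconcile the protocol synopsis, protocol 4.1, protocol 7.1.4 and SAP 2.1 (text and table footnote) so that one trigger defines the as-needed sub-cohorts. The choice belongs to the sponsor. The cost is a wording alignment in four places.

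SAP 4.2.2 describes the conduct of the study in the past tense, so new wording may no longer affect how patients are treated. For those already treated, the clinical study report should:

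- state that both triggers were in force;
- give a descriptive listing for IB and IIB of first anti-diarrheal date against diarrhea onset date and grade;
- interpret the prophylactic versus as-needed comparison in that light.

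The listing costs one output, with limits to be stated. Protocol 7.6.1 records medication name and duration but mentions no indication, and the treatments suggested in protocol 7.1.4 include systemic opioids, so the first anti-diarrheal dose may not always be identifiable. SAP 8.2.4.1 summarizes adverse events by maximum grade, and nothing shows that grade on a given day, or intolerability, is captured.

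The listing should not become a table of outcomes by grade at first dose. That would condition on something that happens after assignment and is itself part of the outcome, so it could not show what the trigger did.
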